8.10.4. Efficacy Analyses

Primary Analysis

The mITT population will be the primary population for the analysis of the efficacy endpoints of the study.

Primary Endpoint

The primary endpoint for this study is the change from baseline in Fatigue Severity Score at Day 28.

Secondary Endpoints

To maintain the trial-wise Type I error rate at 0.05, a closed test procedure will be used for the secondary endpoints. The order of the secondary endpoints will be prospectively specified in the SAP.

Analysis of the secondary and exploratory endpoints will be summarized according to the variable type:

- Continuous data summaries will include:
 - o If the Normality assumption is met, Analysis of Covariance (ANCOVA) would be used.
 - If the Normality assumption is not met, a non-parametric method or a rank ANCOVA analysis i.e., an ANCOVA analysis on rank-transformed data will be used.
- Categorical data summaries will be based on Logit model will be used.
- Time-dependent data: Cox proportional hazards model will be used to analyze time dependent data and to depict the time to event data.

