3.2 Secondary Endpoints

The secondary endpoints for the study are:

• Duration of COVID-19 associated symptoms from start of study treatment (Day 0) based on self-assessment using daily symptom diary

Duration is defined as number of days when any symptoms scored as

- 2 or 3 at baseline are still scored as 2 or 3 (i.e., not 0 or 1) through Day 56, or
- 1 or 0 at study entry are scored as 1 or worse (i.e., not 0) through Day 56.
- Number of symptom-free days of COVID-19 associated symptoms that were present at the start of study treatment (Day 0) based on self-assessment using daily symptom diary *Symptom-free days are defined as number of days when any symptoms scored as* 1, 2 or 3 at baseline are still scored as 0 through Day 56.
- Progression (or worsening) of COVID-19-associated symptoms through Day 56 compared to baseline

Progression or symptom worsening is defined as number of days when any symptoms scored as

- 2 at baseline are still scored as 3 through Day 56, or
- 1 at baseline are still scored as 2 or 3 through Day 56, or
- 0 at study entry are scored as worse (i.e., not 0) through Day 56.
- Change from baseline in PROMIS® Fatigue Score at Days 28 and 56
- Change from baseline in PROMIS® Cognitive Function Score at Days 28 and 56
- Change from baseline in PROMIS® Sleep Disturbance Score at Days 28 and 56
- Incidence of hospitalization during the treatment phase
- Duration (days) of hospitalization during the treatment phase

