4. SAMPLE SIZE DETERMINATION AND RATIONALE

This is a randomized study with two treatment groups. The subjects will be randomized to the treatment groups (leronlimab or placebo) in a 1:1 ratio.

A total of 50 subjects will be randomized in this study. The sample size is based on clinical judgment. No statistical power calculation is used to establish the sample size for this exploratory study.

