7.4 Multiple Comparisons and Type I Error Rate Multiplicity adjustments

There will be no adjustment for multiple testing or multiplicity for this phase II trial. For all effectiveness endpoints, inference will be based on type I error rate of 0.05.

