7.5 Covariates and Prognostic Factors

In the efficacy analysis, the stratification factors and baseline values will be used as covariates in the analysis of all the primary, secondary, and exploratory endpoints.

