8.2.2 Secondary Efficacy Endpoint

8.2.2.1 Duration of COVID-19 associated symptoms from start of study treatment (Day 0) based on self-assessment using daily symptom diary.

Duration is defined as number of days when any symptoms scored as

- 2 or 3 at baseline are still scored as 2 or 3 (i.e., not 0 or 1) through Day 56, or
- 1 or 0 at study entry are scored as 1 or worse (i.e., not 0) through Day 56.

The duration (days) of COVID-19 associated symptoms will be compared between the treatment groups using the a non-parametric method or a rank-ANCOVA analysis i.e., an ANCOVA analysis on rank-transformed data.

8.2.2.2 Number of symptom-free days of COVID-19 associated symptoms that were present at the start of study treatment (Day 0) based on self-assessment using daily symptom diary.

Symptom-free days are defined as number of days when any symptoms scored as 1, 2 or 3 at baseline are still scored as 0 through Day 56.

The number of symptom-free days of COVID-19 associated symptoms will be compared between the treatment groups. Similar analysis methods used for the section 8.2.2.1 will be applied to analyze the data from this endpoint.

8.2.2.3 Progression (or worsening) of COVID-19-associated symptoms through Day 56 compared to baseline.

Progression or symptom worsening is defined as number of days when any symptoms scored as

- 2 at baseline are still scored as 3 through Day 56, or
- 1 at baseline are still scored as 2 or 3 through Day 56, or
- 0 at study entry are scored as worse (i.e., not 0) through Day 56.

The progression (or worsening) of COVID-19-associated symptoms will be compared between the

treatment groups. Similar analysis methods used for section 8.2.2.1 will be applied to analyze the data from this endpoint.

8.2.2.4 Change from baseline in PROMIS® Fatigue Score at Days 28 and 56.

The change from baseline in PROMIS® Fatigue Score will be compared between the treatment groups will be presented and summarized descriptively by treatment group using ANCOVA adjusting for stratification factors. If the data is not normally distributed, a non-parametric method or a rank-ANCOVA analysis i.e., an ANCOVA analysis on rank-transformed data will be used.

8.2.2.5 Change from baseline in PROMIS® Cognitive Function Score at Days 28 and 56.

The change from baseline in PROMIS® Cognitive Score will be compared between the treatment groups. Similar analysis methods used for section 8.2.2.4 will be applied to analyze the data from this endpoint.

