8.2.2.6 Change from baseline in PROMIS® Sleep Disturbance Score at Days 28 and 56.

The change from baseline in PROMIS® Sleep Score will be compared between the treatment groups.. Similar analysis methods used for section 8.2.2.4 will be applied to analyze the data from this endpoint.

8.2.2.7 *Incidence of hospitalization during the treatment phase*

The Incidence of hospitalization will be compared between the treatment groups. Similar analysis methods used for section 8.2.2.1 will be applied to analyze the data from this endpoint.

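### SAP 8.2.2.7 sends a yes/no endpoint, incidence of hospitalization, to a method written for a number of days; this contradicts the protocol's logit model and yields no effect estimate with a confidence interval.

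*Combined protocol and SAP*

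**What the plan says.** SAP 3.2 lists "Incidence of hospitalization during the treatment phase" as a secondary endpoint. For each subject it is yes or no.

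SAP 8.2.2.7 gives no method of its own: "The Incidence of hospitalization will be compared between the treatment groups. Similar analysis methods used for section 8.2.2.1 will be applied". The section it points to, 8.2.2.1, concerns a number of days with symptoms and offers "a non-parametric method or a rank-ANCOVA analysis i.e., an ANCOVA analysis on rank-transformed data". It gives no rule for choosing between the two options. SAP 8.2.2.8, on duration of hospitalization, uses the same cross-reference.

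Protocol 8.10.4 sorts secondary and exploratory endpoints by variable type. For categorical data it says "Categorical data summaries will be based on Logit model will be used"; it reserves rank-ANCOVA for continuous data that are not normal. The SAP neither mentions nor explains the difference.

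Three other SAP statements bear on this endpoint:

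- Section 7.4: "For all effectiveness endpoints, inference will be based on type I error rate of 0.05".
- Section 7.5: "the stratification factors and baseline values will be used as covariates in the analysis of all the primary, secondary, and exploratory endpoints".
- Section 8.1: categorical data are summarised by counts and percentages.

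**The concern.** The method does not suit the data type, and the two documents name different methods. Ranks of a 0/1 variable take only two values, so rank-ANCOVA amounts to a linear model on the 0/1 outcome. Its coefficient is a difference in mean ranks, which has no direct clinical meaning. SAP 8.2.1 plans an odds ratio with a 95% CI for the primary endpoint; nothing comparable is planned here.

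Nor can the analysis be run as written without further choices. One of the two permitted methods is unnamed, and section 7.5 asks for a baseline value as covariate although hospitalization during treatment has none.

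At stake is that the test and the estimate could be settled after unblinding, for an endpoint where a handful of events may fall on either side of 0.05 according to the test used.

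**Working it through.** The documents give no event rate, power or p-value for this endpoint, so there is no planned figure to reproduce.

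**Inputs.** SAP section 4: "A total of 50 subjects will be randomized in this study", allocated 1:1, so 25 per arm. Alpha is 0.05 (SAP 7.4), taken as two-sided because sidedness is not stated. Everyone is assumed analysed. Event counts and rates are assumed scenarios.

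**1. Rank method, 0 versus 4 events.** Mid-ranks of 0/1 data are a linear function of the 0/1 values, so the p-value equals that of a t-test on those values.

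- Difference in proportions: 4/25 − 0 = 0.16.
- Pooled variance: 4 × (1 − 0.16) / 48 = 0.07.
- Standard error: √(0.07 × 2/25) = 0.0748.
- t = 0.16 / 0.0748 = 2.14 on 48 df, p = 0.038.

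**2. Fisher, same table.** 2 × C(25,4) / C(50,4) = 2 × 12,650 / 230,300 = 0.110.

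**3. Other tables and other exact tests** (two-sided, unadjusted):

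| Events | Rank | Fisher | Boschloo | Barnard |
|---|---|---|---|---|
| 0 vs 3 | 0.077 | 0.235 | 0.150 | 0.089 |
| 0 vs 4 | 0.038 | 0.110 | 0.065 | 0.041 |
| 0 vs 5 | 0.018 | 0.0502 | 0.033 | 0.021 |
| 1 vs 6 | 0.042 | 0.098 | 0.065 | 0.053 |
| 2 vs 8 | 0.034 | 0.074 | 0.041 | 0.038 |
| 3 vs 9 | 0.048 | 0.096 | 0.065 | 0.055 |

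If the unnamed option were the Wilcoxon normal approximation, 0 versus 4 would give 0.039. With a two-level stratum covariate (8, 12 or 17 of 25 per arm in one stratum, assumed), rank-ANCOVA gives 0.022 to 0.040 for 0 versus 4.

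**4. Overall type I error**, summed over all tables with 25 per arm and the same rate in both arms:

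| Assumed rate | Rank | Fisher |
|---|---|---|
| 2% | 0.002 | <0.001 |
| 5% | 0.020 | 0.001 |
| 10% | 0.049 | 0.009 |
| 15% | 0.055 | 0.019 |
| 20% | 0.055 | 0.022 |

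**5. Would the protocol's ordinary logit model work?** With no events in one arm the maximum-likelihood odds ratio is not finite. The chance that at least one arm has none is 1 − (1 − (1 − p)²⁵)².

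- 2%: 0.98²⁵ = 0.603, so 1 − 0.397² = 84%.
- 5%: 0.95²⁵ = 0.277, so 1 − 0.723² = 48%.
- 10%: 0.90²⁵ = 0.072, so 1 − 0.928² = 14%.

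**6. What Firth's method gives for 0 versus 4.** Without a stratum term the penalty is equivalent to adding one half to each cell.

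- Odds ratio: (4.5 × 25.5) / (0.5 × 21.5) = 10.7.
- Fitted proportions: 0.5/26 and 4.5/26; under no effect, 5/52 in both arms.
- Penalised log-likelihoods: −14.450 and −16.461.
- Likelihood ratio: 2 × 2.011 = 4.02 on 1 df, p = 0.045.
- Profile 95% CI: 1.05 to about 1,445.

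The estimate is finite and the interval shows how little four events tell us.

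**The case against.** A reader might infer that the rank method produces significant results which exact testing does not support, and so false positives. The figures do not bear this out. Fisher is the most conservative comparator in the table. For 0 versus 4, Barnard's exact test gives 0.041, close to the rank value; for 0 versus 5 and 2 versus 8, both Barnard and Boschloo fall below 0.05. The rank method's overall type I error stays below 0.05 at 2%, 5% and 10%. The gap from Fisher is mainly Fisher's conservatism.

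The discordant tables may also be rare. With three or fewer events in total neither test can reach 0.05, and under equal rates that happens 98% of the time at 2% and 76% at 5%.

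It would also be too strong to say that the SAP prescribes rank-ANCOVA. Section 8.2.2.1 allows an unnamed alternative and 8.2.2.7 asks only for similar methods, so an exact test is not ruled out. Counts and percentages are already planned in SAP 8.1, and a crude risk difference follows from them. The trial is exploratory and unpowered, and this is one of eight secondary endpoints. The absence of multiplicity control is a separate matter.

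All of this limits the size of the problem. The mis-assigned method, the conflict with the protocol and the missing interval estimate remain.

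**Conclusion.** The point holds as one of specification. SAP 8.2.2.7 assigns a days-based method to a binary endpoint, contradicts protocol 8.10.4 without comment, and plans no odds ratio or risk difference with a confidence interval. This follows from the text and needs no assumed event rate.

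The numerical consequence is narrower. In some sparse tables the conclusion depends on the test chosen: 0.038 by ranks against 0.110 by Fisher for 0 versus 4, with other exact tests in between. There is no material inflation of type I error: at most 0.049 at 2%, 5% and 10%, about 0.055 at 15-20%. Simply restoring the ordinary logit model would not be enough, since an arm without events is likely or plausible at low rates (84%, 48% or 14%).

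These figures assume 25 analysed per arm, two-sided tests, no stratum term except where stated, and event rates that the documents do not supply. The change should be made before unblinding; it does not call the design into question.

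**What to change.** Replace the cross-reference in SAP 8.2.2.7 with one named analysis: Firth penalised logistic regression on treatment arm and symptom-duration stratum, reporting the odds ratio, its profile-likelihood 95% CI and the p-value. State that no baseline covariate applies. This stays within the protocol's logit framework and remains estimable when one arm has no events.

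Beside the counts and percentages already planned in SAP 8.1, add the risk difference with an exact 95% CI. Say that the Firth p-value is the test of record, because the exact interval may disagree with it near 0.05. Keep the rank method for 8.2.2.8 (duration) only.

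The cost is one SAP subsection, with no change to data collection, design or sample size. The downside is that intervals will be wide with few events. The change should not be presented as a stricter test: for 0 versus 4 Firth also falls just below 0.05. What it adds is a method suited to the data, fixed in advance, with an interpretable estimate.

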8.2.2.8 Duration (days) of hospitalization during the treatment phase

The duration of hospitalization will be compared between the treatment groups. Similar analysis methods used for section 8.2.2.1 will be applied to analyze the data from this endpoint.

8.2.3 Exploratory Endpoints

- Change from baseline in pulse oxygen saturation (SpO2) at Day 7, 14, 21, 28, 35, 42, 49, and 56 The Change from baseline in pulse oxygen saturation (SpO2) will be presented and summarized descriptively by treatment group using similar analysis methods used for section 8.2.2.4.
- Change from baseline in serum cytokine and chemokine levels on Days 28 and 56

 The Change from baseline in serum cytokine and chemokine levels will be presented and summarized descriptively by treatment group compared using using similar analysis methods used for section 8.2.2.4.
- Change from baseline in CD4+ and CD8+ T cell count on Days 28 and 56

 The Change from baseline in CD4+ and CD8+ T cell count will be presented and summarized

descriptively by treatment group compared using similar analysis methods used for section 8.2.2.4.

Change from baseline in Transgrowth factor beta 1 (TGF beta1) on Days 28 and 56
 The Change from baseline in Transgrowth factor beta 1 (TGF beta1) will be presented and summarized descriptively by treatment group compared using using similar analysis methods used

for section 8.2.2.4.

Change from baseline in CRP on Days 28 and 56

The Change from baseline in CRP will be presented and summarized descriptively by treatment group compared using similar analysis methods used for section 8.2.2.4.

• Change from baseline in CCR5 receptor occupancy on Days 28 and 56.

The Change from baseline in CCR5 will be presented and summarized descriptively by treatment group compared using similar analysis methods used for section 8.2.2.4.

 To explore biomarkers that may predict and/or act as pharmacodynamic indicators of pharmacologic activity of leronlimab.

Biomarkers that may predict and/or act as pharmacodynamic indicators of pharmacologic activity of leronlimab will be explored.

• Evaluation of Global Health Assessment at Day 56.

The change from baseline in Global Health Assessment will be compared between the treatment groups. Similar analysis methods used for section 8.2.2.4 will be applied to analyze the data from this endpoint.

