If Visit 2 (V2) takes place on the same day as the Screening Visit (V1), scheduled assessments performed under screening (V1) do not need to be repeated at V2. Subjects will be given a diary to record all symptoms daily throughout the entire treatment period starting at baseline.

Treatment Groups

IP Study Dosage **Dosing Frequency and Amount** Form concentration

Table 4-1:

Route of Drug Administration Parenteral 2 injections of PRO 140 (2 X 2 mL/inj.) PRO 140 175 mg/mLSC injection (700 mg)solution per week on opposite sides of abdomen 2 injections of placebo (2 X 2 mL/inj.) Parenteral 0 mg/mLSC injection Placebo solution per week on opposite sides of abdomen

At V2, subjects will be randomized to receive leronlimab (PRO 140) or placebo which will be administered subcutaneously weekly at V2, V4, V6, V8, V10, V12, V14, and V16.

The following assessments will be performed at V4, V6, V8, V10, V12, V14, V16, and V17(EOT): vital signs, pulse oxygen saturation, physical examination, electrocardiogram (ECG (V17 only), PROMIS® Fatigue Scale, PROMIS® Cognitive Function- Short Form 4a, PROMIS® Sleep Disturbance – Short Form 4a, Global Health Assessment (V17 only), blood sample collection for routine serum biochemical, hematologic, coagulation and urine laboratory assessments (V10 and V17). CD4+ and CD8+ T cell count and serum cytokine and chemokine levels (V10 and V17), assessment for the requirement of hospitalization and patient compliance to daily diary completion will be checked by the site staff.

Additionally, telephone or video contact visits will be performed 3 days (±1 day) after each treatment administration visit. The requirement of hospitalization and patient compliance to daily diary completion will be checked during V3, V5, V7, V9, V11, V13, and V15 via telephone.

Adverse events and concomitant medications will be monitored throughout the study.

Follow Up Period (4 weeks after EOT± 3 days)

Follow-up visit (V18) will be performed 4 weeks after the End of Treatment (EOT) visit. The following assessments will be performed at V18: vital signs, physical examination, pulse oxygen saturation, blood sample collection for immunophenotypic biomarker analysis, assessment for the requirement of hospitalization, review of adverse events and concomitant medications.

Note: During visits conducted at the study clinic, subjects and site personnel will use appropriate protective gear (e.g., masks, gloves) to prevent the spread of the infection.

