Window Period		Within 7 days of the Screening Visit	3(±1) days after V2	7(±1) days after V2	3(±1) days after V4	7(±1) days after V4	3(±1) days after V6	7(±1) days after V6	3(±1) days after V8	7(±1) days after V8	3(±1) days after V10	7(±1) days after V10	3(±1) days after V12	7(±1) days after V12	3(±1) days after V14	7(±1) days after V14	7(±1) days after V16	28(±3) days after V17
Urine Pregnancy Test [12]	X	X								X							X	
Urinalysis [13]	X									X							X	
CD4+ and CD8+ T cell count		X								X							X	
Serum cytokine and chemokine levels [14]		X								X							X	
CCR5 Receptor Occupancy		X								X							X	
Immunophenotypic Biomarker Analysis		X								X							X	X
Randomization [15]		X																
PRO 140 (700 mg) or Placebo Administration		X		X		X		X		X		X		X		X		
Assessment for Requirement of Hospitalization			X	X	х	X	х	X	x	X	х	X	х	х	X	X	X	x
Concomitant Medications	X	X	X	X	X	X	X	X	X	X	X	X	X	X	X	X	X	X
Adverse Events			X	X	X	X	X	X	X	X	X	X	X	X	X	X	X	X

- [1] Informed consent must be obtained prior to patient participation in any protocol-related activities that are not part of routine care.
- [2] Initial evaluation of patient eligibility will be performed by Investigator.
- [3] Medical history and current therapies (medications and non-medications).
- [4] Symptom-directed physical examination
- [5] Pre-treatment and post-treatment vital signs and SpO2 will be recorded at V2. Post-treatment vital signs and SpO2 will be recorded at V4, V6, V8, V10, V12, V14, and V16. Vital Signs will include blood pressure, heart rate, respiration rate, temperature, weight, and height. (Note: Height will be measured only at V1).
- [6] Symptom Score will be assessed for patient eligibility based on symptom score for following symptoms consistent with COVID-19 as a result of confirmed SARS-CoV-2 infection for a prolonged period of time (>12 weeks) (Total Clinical Symptom Score of ≥6 with at least two symptoms of moderate or higher severity at the time of Screening (at V1) and prior to Randomization (at V2)
- [7] Patients will be asked to complete a daily diary during the treatment phase to record symptoms.
- [8] All three questionnaires, PROMIS® Fatigue Scale, PROMIS® Cognitive Function, and PROMIS® Sleep Disturbance will be evaluated before study drug administration.
- [9] Hemoglobin, Hematocrit (HCT), Red Blood Cells (RBC), White Blood Cells (WBC) with total and differential count, Absolute Neutrophil Count (ANC) and platelets.
- [10] Biochemistry

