7.19. GLOBAL HEALTH ASSESSMENT

The brief questionnaire evaluates general health (physical and mental health) and quality of life. This is an exploratory (non-validated) assessment developed (based on PROMIS® Scale v1.2 – Global Health) with an intent to assist in identifying more appropriate global health measurement for the future studies in long-hauler COVID-19 population and will not be used for labeling claims. The assessment will be performed (self-administered by the subject) at V17 (EOT/Day 56). See Appendix 6.

CONFIDENTIAL Page 67 of 101

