3.3 Exploratory Endpoints

• Change from baseline in pulse oxygen saturation (SpO2) at Day 7, 14, 21, 28, 35, 42, 49, and 56

- Change from baseline in serum cytokine and chemokine levels on Days 28 and 56
- Change from baseline in CD4+ and CD8+ T cell count on Days 28 and 56
- Change from baseline in Transgrowth factor beta 1 (TGF beta1) on Days 28 and 56
- Change from baseline in CRP on Days 28 and 56
- Change from baseline in CCR5 receptor occupancy on Days 28 and 56.
- To explore biomarkers that may predict and/or act as pharmacodynamic indicators of pharmacologic activity of leronlimab.
- Evaluation of Global Health Assessment at Day 56

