7. DATA CONVENTION AND RELATED DEFINITIONS

7.1 Baseline Definition

For all parameters, baseline will be defined as the last available value before the randomized treatment.

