7.7.3 Change from Baseline

For any of the effectiveness measurements change from baseline will be calculated using the formula noted below.

Change from baseline =

Post Baseline Measurement – Baseline Measurement

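### The SAP plans a change-from-baseline analysis of the Global Health Assessment, but the form is completed only at Day 56, so no subject can have a change score

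*Combined protocol and SAP*

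**What the plan says.** The endpoint lists in the protocol (synopsis and 8.2.3) and in SAP 3.3 give this item as "Evaluation of Global Health Assessment at Day 56". Its bullet heading in SAP 8.2.3 repeats that label, but the sentence beneath it says "The change from baseline in Global Health Assessment will be compared between the treatment groups" and sends the reader to the methods of SAP 8.2.2.4, which are ANCOVA or, for non-normal data, a non-parametric method or rank-ANCOVA.

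On data collection, protocol 7.19 says: "The assessment will be performed (self-administered by the subject) at V17 (EOT/Day 56"). The protocol synopsis, protocol section 4 and SAP 2.2 all carry the restriction "Global Health Assessment (V17 only").

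Three general SAP rules apply to any change endpoint:

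- SAP 7.1: "For all parameters, baseline will be defined as the last available value before the randomized treatment".
- SAP 7.7.3 defines change as "Post Baseline Measurement – Baseline Measurement".
- SAP 7.5 says that "the stratification factors and baseline values will be used as covariates in the analysis of all the primary, secondary, and exploratory endpoints".

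**The concern.** A change score needs two measurements and this form is given once. The planned quantity therefore cannot be derived, and the general covariate rule asks for a second quantity that will not exist.

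If this stands, whoever programs the analysis must replace both the outcome and the model with something the SAP does not describe. If that happens after unblinding, the choice is made with treatment codes in hand. SAP 7.4 bases inference on every effectiveness endpoint on a type I error rate of 0.05 with no multiplicity adjustment, so a p-value from the improvised analysis could still be reported as if it had been planned.

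**Working it through.** The plan states no calculated figure for this endpoint. The check is a count of scheduled administrations, followed by the SAP's own definitions.

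**Step 1: when the form is completed.**

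| Source | Global Health Assessment |
|---|---|
| Protocol synopsis; protocol section 4; SAP 2.2 (prose) | V17 only |
| Protocol Table 4-2; SAP Table 2-1 | one mark, no other visit |
| Protocol 4.2.1 (V2, before first dose) | not listed |
| Protocol 4.2.3 (V4 to V16) | not listed |
| Protocol 4.2.4 (V17, end of treatment) | listed |
| Protocol 7.19 | V17, Day 56 |

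The PROMIS forms show the contrast. A footnote to both schedules says "All three questionnaires, PROMIS® Fatigue Scale, PROMIS® Cognitive Function, and PROMIS® Sleep Disturbance will be evaluated before study drug administration", and protocol 7.16 to 7.18 schedule each of them from V2 onward. The Global Health Assessment is not among them. The restriction to V17 appears in running prose in several places, so it does not depend on how a table was laid out.

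Count: administrations before the first dose = 0; administrations in total = 1.

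**Step 2: apply the definitions.**

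- Baseline (SAP 7.1) is the last value before randomized treatment. With no administration before treatment, it is undefined for every subject.
- Change (SAP 7.7.3) is the post-baseline value minus baseline. The first term can exist at Day 56; the second cannot.
- Planned sample (SAP 4): 50 subjects, 1:1, so 25 per arm. Subjects with a computable change: 0 of 50. Subjects who could have a Day 56 score if all complete V17: up to 50 of 50.

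**Step 3: the model.** SAP 8.2.2.4 names adjustment for stratification factors. SAP 7.5 adds the baseline value for all exploratory endpoints. The symptom-duration stratum is available for this endpoint; the baseline value is not.

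**Step 4: whether imputation could rescue it.** SAP 7.3 imputes nothing, while protocol 8.9.3 foresees multiple imputation for efficacy data. The two disagree, but it makes no difference here. A value that was never scheduled is not missing in the ordinary sense, and an imputation model would have no observed baseline on this form from any subject.

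**Step 5: internal consistency.** In SAP 8.2.3 the measured exploratory endpoints other than this one are headed as changes from baseline and analysed as such. This one is headed as a Day 56 evaluation and analysed as a change. The analysis sentence, not the endpoint definition, is the part out of line.

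**The case against.** The strongest reply is that this is a drafting slip with little consequence. Protocol 7.19 describes the form as exploratory and non-validated, intended to help choose a better global measure for later studies, and not for labeling. No primary, secondary or safety conclusion depends on it. The change wording was probably carried over from the neighbouring bullets. With it struck out, a Day 56 comparison by ANCOVA adjusted for the stratum remains, which is nearly a complete plan. Protocol 8.10 requires the SAP to be approved before database lock, and SAP 2.8.2 places unblinding after lock, so the wording can be corrected blind.

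Most of this stands. The impact is small, and a post hoc choice is avoidable. But it is avoided only if the text is corrected in time; until then the written rule cannot be executed and conflicts with SAP 7.5 as well.

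A second reply is that the form might ask patients to rate their own change. I could not see the form (protocol Appendix 6), so this cannot be excluded. Such an item would be a transition rating made at Day 56. It would not be the subtraction defined in SAP 7.7.3 and would supply no baseline covariate.

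**Conclusion.** The concern holds. The Global Health Assessment analysis in SAP 8.2.3 cannot be run as written: 0 of 50 subjects can have a computed pre-to-post change, and the baseline covariate is absent for all of them. This rests on the visit schedule being followed as written, with no unscheduled pre-dose administration of the form.

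The effect is confined to one exploratory endpoint. The data that will be collected do support a comparison of Day 56 scores, and randomization makes that a fair comparison between arms. What cannot be recovered is adjustment for a chance difference in starting global health, which is possible with 25 subjects per arm.

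**What to change.** Make the correction before database lock and unblinding.

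1. **SAP 8.2.3.** Replace the change-from-baseline sentence with a between-arm comparison of the Day 56 Global Health Assessment score, with treatment arm and symptom-duration stratum in the model. The simplest choice is the ANCOVA already named in SAP 8.2.2.4. If the score is treated as ordered categories, an ordinal model with the same two terms is the alternative. Name one of these as the planned model, and state which score is analysed.
2. **SAP 7.5.** Add an exception saying that no baseline covariate applies to this endpoint.

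The cost is about two sentences in the SAP. The protocol need not change, because its endpoint is already a Day 56 evaluation.

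If change from baseline is really intended, add the form at V2 before dosing, alongside the three PROMIS questionnaires. That costs one short extra questionnaire and a protocol amendment with IRB approval, and it yields change scores only for subjects not yet dosed when it takes effect.
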